#### 5.11.3.1.1 Prediction Step

The prediction step attempts to predict the biochemical response based on observed data that may have an influence on it (assuming MAR).

The prediction model will include the following variables, to attempt to estimate the missing value as closely as possible based on available characteristics.

Timepoint	Variables
Variable Used for Randomization (per IWRS)	• Fludrocortisone replacement status (requires fludrocortisone or does not require fludrocortisone)
Baseline Assessments	

Participant's assessment of biochemical control

Sex

Assessments at V4, V5, V6 and V7	Participant's biochemical response status
Other	Randomized study treatment (Chronocort or IRHC)

#### 5.11.3.1.2 Multiple Imputation Step for All Missing Data (MAR)

Within the Bayesian framework, the task of imputing missing values is achieved by drawing random values from the posterior predictive distribution of the missing primary efficacy endpoint data (predicted by the logistic regression prediction model specified above). This posterior predictive distribution is a function of the observed data and regression parameters (or function of regression parameters) under MAR conditions.

When the last variable in the sequence of variables listed above in the prediction model has been imputed, the algorithm cycles again through each variable, repeating the chain of regression estimation and imputation draw steps. These cycles are repeated 200 times ("burn-in" iterations) and finally there will be 50 draws from the predictive distribution for missing values. SAS PROC MI will be used for this process.

Example SAS Code for Prediction and Imputation Steps:

The LOGISTIC option LIKELIHOOD=AUGMENT may be used when the maximum likelihood parameter estimates do not exist. This option adds observations in each response group to the likelihood function. Each added observation contributes the same weight, with the number of

parameters in the logistic regression model as the total added weight. Existence of maximum likelihood estimates will be checked after general unblinding with the actual randomization.

# 5.11.3.1.3 Analysis Step

Each of the imputations will be analyzed using a logistic regression model, as described in Sections 5.11.4.1 and 11.2.

# 5.11.3.1.4 Combining Step

SAS Proc MIANALYZE will be used to combine the 50 point estimates for the common response probability difference and standard errors, allowing appropriate statistical inference as described below:

# 5.11.3.2 First Key Secondary Efficacy Endpoint – Dose Response at Visit 6

The approach for dose response will be similar to that described in Section 5.11.3.1 for biochemical response. The primary analysis conducted using MAR approach for imputation will be presented for this endpoint, similar to the primary efficacy endpoint.

# 5.11.3.3 Second Key Secondary Efficacy Endpoint – Total Daily Dose of Hydrocortisone at 28 weeks

For the second key secondary efficacy endpoint, where an ICE occurs, every effort will be taken to ascertain the total daily dose of hydrocortisone (or equivalent) at 28 weeks whether on study or not. Where hydrocortisone is not used, and instead an alternative treatment (such as prednisone, prednisolone or dexamethasone) is received, the dose of the treatment received will be converted to hydrocortisone equivalent as follows [Nebesio et al. 2016]:

- Dexamethasone x 80
- Prednisolone/one x 5

This could occur at pre Run-in Baseline, and for participants that discontinue study treatment.

Where missing data exists for total daily hydrocortisone dose after discontinuation, no explicit imputation will be done.

#### 5.11.4 Analysis of the Primary Efficacy Endpoint

#### 5.11.4.1 Main Analysis of the Primary Efficacy Endpoint

The main analysis of the primary endpoint is based on the proportion of participants achieving biochemical response at V6, with ICE handling per Section 5.11.2.1 and imputing missing data using the MI approach described in Section 5.11.3.1.

The primary estimand will be analyzed using a logistic regression model. The model will include the following factors: treatment arm (Chronocort versus IRHC, reference IRHC), the participant's fludrocortisone replacement status at baseline (requires fludrocortisone or does not require fludrocortisone) and whether they are in biochemical control at baseline or not (based on the androgen results from the baseline visit [Visit 2]), plus the interaction of these variables. The estimated response rate for each treatment arm, and the corresponding difference in rates along with the 2-sided 95% CI for the difference will be presented using the procedure described by Ge et al. (2011). See Section 11.2 for further details of the analysis.

- In case issues related to convergence of the model or other issues that may be expected based on the frequency counts within the combinations of the factors involved lead to warnings (such as, for example, complete or quasi- separation, model less than full rank, etc.) and/or prevent the model from producing valid results (execution stops, some terms in the model not estimated, unusually large standard errors obtained, etc.), an initial assessment of the distribution of response/non-response outcomes will occur in order to ascertain the possible best next steps. However, a priori, in lieu of such knowledge, the following steps will be implemented in order specified below: Exclude the interaction term;
- Exclude the interaction term and one of the main effects (fludrocortisone replacement status at baseline or biochemical control at baseline, whichever produces combinations with lower counts);
- 3) Exclude both factors and their interaction.

At each step, the model will be rerun and evaluated for continued occurrence of issues. The decisions made at each step of the model selection process will be fully documented.

17-OHP and A4 results will be listed, and results from visits outside the protocol specified visit window will be flagged.

#### 5.11.4.2 Sensitivity and Supportive Analyses

The main statistical analysis assumes that the treatment effect is constant over the standard explanatory variables. Additional sensitivity analyses will investigate whether the treatment

effect varies with the explanatory variables: including, but not limited to, subgroup analyses by biochemical control status at baseline, fludrocortisone use at baseline, region or country as appropriate and pre-treatment corticosteroid. Separate summary tables will be presented for each subgroup and a measure of treatment-by-subgroup interaction together with confidence interval and P-value provided. Forest plots will additionally be presented to provide a visual comparison of the differences in treatment effect between subgroups.

All subgroup analyses will be performed as unstratified/unadjusted.

Summary tables split by biochemical control at baseline will also be presented for disposition, demography and baseline characteristics and exposure to study drug, (Participants with baseline 17-OHP equal to or below the upper limit for optimal control at 08:00 hours and baseline A4 equal to or below the upper limit of the reference range will be classified as 'in biochemical control'. Participants with baseline 17-OHP above the upper limit for optimal control and/or baseline A4 above the upper limit of the reference range will be classified as 'not in biochemical control'.)

Supportive analysis: The main statistical analysis will additionally be performed on the EES.

Other analyses: Any other analyses of 17-OHP and A4 concentrations and dose, not otherwise specified as a secondary analysis, are supplementary analyses. The number and percentage of participants in receipt of rescue medication overlapping with a scheduled visit, as well as the number and percentage of participants with moved Visit 6 assessment due to stress dosing rules will be summarized by treatment group, split by baseline biochemical control status.

All observed data for the primary endpoint will additionally be summarized descriptively by visit, with no imputation.

# 5.11.5 Key Secondary Efficacy Endpoints and Analyses

The high-level handling approaches for the secondary endpoints are as follows. All observed data for these endpoints will additionally be summarized descriptively by visit, with no imputation.

Endpoint	Analysis Set	Modelling Method	Data Handling
Percentage of Participants Dose	FAS and EES	Logistic Regression	As per Primary efficacy endpoint.
Response after 28 Weeks of Randomized Study Treatment			

Endpoint	Analysis Set	Modelling Method	Data Handling
Mean Total Daily Dose after 28 Weeks of Randomized Study Treatment	FAS and EES	MMRM	Treatment policy strategy for participants who stop treatment before visit 6. Treatment policy strategy for participants whose visit 6 is delayed because of administering rescue medication. Present all visits up to and including V6.

# 5.11.5.1 Percentage of Participants Achieving Dose Response after 28 Weeks of Randomized Study Treatment

The percentage of participants achieving dose response over the course of the study will be analyzed in a similar manner to the primary efficacy endpoint (logistic regression) on the FAS.

# 5.11.5.2 Mean Total Daily Dose after 28 Weeks of Randomized Study Treatment

Mean Total Daily Dose will be analyzed on the FAS using a repeated measures mixed model with factors for treatment arm (Chronocort versus IRHC, reference IRHC), the participant's fludrocortisone replacement status at baseline (requires fludrocortisone or does not require fludrocortisone) and whether they are in biochemical control at baseline or not (based on the androgen results from the baseline visit [Visit 2]) and their interaction, as well as the treatment-visit interaction. A restricted maximum likelihood method will be specified, along with an unstructured covariance matrix. The estimate of the least-squared means difference at each visit and the corresponding 95% CI for the difference will be presented. Example SAS code for the analysis is provided in Section 11.3.

Considerations for model adjustments specified in Section 5.11.4 also apply to the analysis of this key secondary efficacy endpoint.

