4.2. Titration Rules

The aim of titration is to establish participants on the lowest dose of glucocorticoid which will provide adequate adrenal replacement and control androgens. At each titration visit during the titration period, adrenal insufficiency symptoms will be collected using the adrenal insufficiency checklist (Appendix 5) and androgen results will be assessed at 08:00 and 13:00 hours. The adrenal insufficiency checklist should only be used to determine if symptoms of under- or over-replacement of glucocorticoids have occurred since the last visit and this questionnaire should not be used to record AEs due to other causes. The analysis of all 17-OHP and A4 levels will be conducted by a central laboratory and the results will be sent to an independent blinded physician, with the independent blinded physician being unaware of the participant's treatment allocation. The independent blinded physician will decide if the dose should be maintained or if a dose reduction is needed and the appropriate packs will be sent to the participant, either to collect from their local study site or sent directly to the participant's home. The treatment packs for each participant will always contain the same number of capsules as the previous supplies (with placebo capsules masking any changes), thus ensuring the participant is not aware of any dose changes.

If the independent blinded physician considers a dose reduction is necessary, a maximum dose reduction of 5 mg is allowed at each titration visit at Weeks 4, 10, and 16. The independent blinded physician will inform the IRT system of the recommended dose changes or that the dose does not need to be changed, which will then inform the pharmacist which IMP packs to dispense based on previous titrations according to the titration rules. The total daily dose must not exceed 30 mg and the afternoon IRHC dose must not exceed 10 mg at any point.

For all dose reductions, the results from the 08:00 hours androgen sample will be used to guide adjustment of the Chronocort night-time dose and IRHC morning dose, and the 13:00 hours androgen sample will be used to guide adjustment of the Chronocort morning dose and the IRHC afternoon dose. If 17-OHP is <300 ng/dL (the upper limit of the reference range) and A4 is <150 ng/dL for males and <200 ng/dL for females (sex-specific upper limit

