# **3** SAMPLE SIZE

Sufficient participants will be screened to achieve approximately 50 participants randomly assigned to either Chronocort or IRHC (25 participants per treatment arm, regardless of baseline strata), or until a cut-off date of 30 April 2023, whichever is reached first. Individual study sites should not randomize more than 8 participants without first consulting the Sponsor. A sample size of 25 participants per treatment arm will provide at least 80% power to demonstrate non-inferiority of Chronocort to IRHC when the biochemical response rate in the IRHC arm is 40%, the non-inferiority margin is 15%, and the biochemical response rate in the Chronocort arm is 68% using a 1-sided continuity corrected z-test with unpooled variance and a 1-sided alpha of 2.5%. Sample size is calculated using PASS 2022 (v22.0.3).

Note: Basing the sample size calculation on a continuity corrected z-test provides a conservative estimate of sample size relative to the test, based on a logistic model adjusted for stratification factors, which will actually be used.

**Note:** Post-hoc analysis of study DIUR-005 showed that ~40% of participants receiving the control treatment (that is: their pre-randomization treatment) would have been down-titrated by the proposed rules for the current study at four weeks after randomization. Estimating therefore the response rate for the IRHC as 40% and expecting that no participants withdrawn completely from hydrocortisone treatment would qualify for down-titration, the estimated treatment benefit of IRHC is a gain in response rate of 40%. Setting the non-inferiority margin as minus 15% thus retains five eighths of the anticipated treatment benefit of IRHC.

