# 4 RANDOMIZATION & UNBLINDING

This is a double-blinded study with 2 treatment arms. The blinded treatment to be taken by a participant will be assigned using an IRT on a 1:1 basis (Chronocort:IRHC). Before the study is initiated, the login information and instructions for use of the IRT will be provided to each site. The randomization list will be generated by the study statistician using a computer-generated central randomization list using balanced blocks. The site will access the IRT at the baseline visit (Day 1) and they will record the randomization number allocated to the participant on the applicable eCRF. Randomization will be balanced within site and stratified by the participant's fludrocortisone replacement status (requires fludrocortisone/does not require fludrocortisone).

Potential bias will be reduced by the following steps:

- Records will be kept of any participants screened, whether or not they enter the study. This will enable an assessment of the representative nature of the participants randomized.
- Both study treatments will be over-encapsulated so that they look the same, so both the participant and the Investigator will not know which treatment group the participant has been randomized to.
- The titration of each participant's dose of study treatment will be the same in both arms and will be based on the adrenal insufficiency checklist and androgen sampling, thus ensuring that opportunities for optimization and control of androgens are the same in both arms.
- The dose titration decisions will be made by an independent blinded physician who will be unaware of the treatment allocation to each participant.
- The treatment packs for each participant will be pre-packed and packs issued by the IRT to ensure that each participant receives the correct number of active and placebo capsules.

After each visit, new supplies will be provided to the participant that contains the same number of capsules as the previous supplies (with placebo capsules masking any changes), regardless of whether the dose was titrated or not, thus ensuring the participant is not aware of any dose changes.

- The primary endpoint is an objective biochemical measure that is not subject to bias.
- Efforts will be made to ensure that all participants remain in the study and are evaluable.
- There will be rigorous monitoring of sites to ensure compliance with all study procedures.

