# 5.11.1.3 Second Key Secondary Efficacy Endpoint: Mean Total Daily Dose of Hydrocortisone after 28 Weeks of Randomized Study Treatment

The second key secondary null hypothesis is that the mean total daily dose of hydrocortisone after 28 weeks of randomized treatment in the Chronocort arm is higher than or equal to the mean total daily dose after 28 weeks of randomized treatment in the IRHC arm. The second key secondary alternate hypothesis is that the mean total daily dose after 28 weeks of randomized treatment in the Chronocort arm is lower than the mean total daily dose after 28 weeks of randomized treatment in the IRHC arm.

Superiority of Chronocort to IRHC (with respect to the total daily dose after 28 weeks of randomized treatment) will be declared if the two-sided 95% CI for the difference in means between the 2 treatment arms (Chronocort minus IRHC) is wholly below zero, provided that biochemical non-inferiority of Chronocort to IRHC has been declared under the primary efficacy objective, and dose superiority of Chronocort to IRHC has been declared under the first key secondary efficacy objective.

Analysis	Statistical Analysis Methods
Primary analysis	Non-inferiority: a 95% CI will be calculated for the difference (Chronocort minus IRHC) in biochemical responder rates. Biochemical non-inferiority will be declared if the 95% CI lies wholly above minus 15%. The primary analysis will be conducted using the FAS.
First key secondary analysis	Superiority analysis: a 95% CI will be calculated for the difference (Chronocort minus IRHC) in dose responder rates. Dose superiority will be declared if the 95% CI lies wholly above zero, provided that biochemical non-inferiority of Chronocort to IRHC has been declared under the primary efficacy objective. The first key secondary analysis will be conducted using the FAS.
Second key secondary analysis	Superiority analysis: a 95% CI will be calculated for the difference (Chronocort minus IRHC) in mean total daily dose after 28 weeks of randomized treatment. Superiority with respect to total daily dose after 28 weeks of randomized treatment will be declared if the 95% CI lies wholly below zero, provided that biochemical non-inferiority of Chronocort to IRHC has been declared under the primary efficacy objective and dose superiority of Chronocort to IRHC has been declared under the first key secondary objective. The second key secondary analysis will be conducted using the FAS.

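### The total-daily-dose model uses baseline androgens only as a yes/no control status (17-OHP cut 1200 ng/dL) although reductions are triggered below 300 ng/dL; adding log baseline 17-OHP would recover a modest amount of precision

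*SAP*

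**What the plan says.** SAP 5.11.5.2, with the estimand table in SAP 5.11.2.3, analyses total daily dose at Weeks 10, 16 and 28 by a REML repeated measures model with unstructured covariance. The terms are treatment, visit, treatment by visit, fludrocortisone status, "whether they are in biochemical control at baseline or not (based on the androgen results from the baseline visit [Visit 2"]), and the interaction of the last two. No continuous androgen value appears, and no covariate-by-visit term is listed.

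SAP Section 2 and SAP 5.11.6.1 define control at 08:00 as 17-OHP no higher than 1200 ng/dL together with A4 no higher than its limit (150 ng/dL in men, 200 in women). A participant who fails on either analyte is coded as not in control.

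Protocol 4.2 sets the biochemical condition for a reduction: "If 17-OHP is <300 ng/dL (the upper limit of the reference range"), with A4 below the same sex-specific limits. A reduction is 5 mg. The 08:00 and 13:00 samples guide different doses, and symptoms of adrenal insufficiency block titration. Everyone starts randomized treatment at 30 mg (Protocol 6.1).

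Superiority on dose is declared when "the two-sided 95% CI for the difference in means" lies wholly below zero, after success on the primary and first key secondary endpoints (SAP 5.11.1.3).

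**The concern.** With a common starting dose there is no baseline dose to adjust for, so baseline androgens are the natural prognostic measure. Everyone coded as in control already has A4 within essentially the trigger's own limits. Inside that group, whether the baseline 08:00 sample would meet the biochemical trigger turns on 17-OHP below 300 versus 300–1200 ng/dL, and the binary factor cannot see this difference. Among those not in control, it also ignores how far 17-OHP lies above the cut.

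Randomization is stratified by fludrocortisone status, not by androgens. With 25 per arm, the standard error of the between-arm difference in mean log 17-OHP is sqrt(2/25) = 0.28 SD, so chance imbalance is likely and a yes/no term corrects it only in part. What is at stake is the width of one confidence interval in a trial of about 50 participants, for an endpoint with no stated power.

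**Working it through.** **1. The plan's own figure.** The only power statement concerns the primary endpoint: "A sample size of 25 participants per treatment arm will provide at least 80% power to demonstrate non-inferiority", where "the biochemical response rate in the IRHC arm is 40%, the non-inferiority margin is 15"%, "the biochemical response rate in the Chronocort arm is 68"%, using a "1-sided continuity corrected z-test with unpooled variance and a 1-sided alpha of 2.5"%. Allocation is 1:1.

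Power = Φ((0.68 − 0.40 + 0.15 − 1/25) / sqrt((0.40×0.60 + 0.68×0.32)/25) − 1.960) = Φ(0.39/0.1353 − 1.960) = Φ(0.923) = 82.2%.

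This reproduces. The documents give no SD, expected difference or power for total daily dose, so the rest uses stated assumptions.

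**2. Analytic bound.** Let ρ be the correlation between log baseline 17-OHP and Week-28 dose, and q the share in control, treating control as a cut on 17-OHP alone. The binary split captures a fraction λ = φ(c)²/(q(1−q)) of ρ², where c is the normal quantile of q. Adding the log value changes the residual variance by the factor (1−ρ²)/(1−λρ²), times a penalty of about 1.024 (43/42) for one more parameter.

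With q = 0.40, λ = 0.622. At ρ = 0.5 the factor is 0.75/(1 − 0.622×0.25) = 0.888, and 0.888×1.024 = 0.909, a 9.1% reduction.

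| ρ | Variance reduction, q = 0.40 | CI-width reduction |
|---|---|---|
| 0.2 | −0.8% (a loss) | −0.4% |
| 0.3 | 1.3% | 0.7% |
| 0.4 | 4.5% | 2.3% |
| 0.5 | 9.1% | 4.6% |
| 0.6 | 15.6% | 8.1% |
| 0.7 | 24.9% | 13.3% |

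With q = 0.20 the variance change runs from −0.3% to 31.3%.

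**3. Simulation of the titration rule.** There were 50 participants per trial, 1,500 trials in each of 16 scenarios, and the SAP's covariates with and without log 08:00 17-OHP. Taken from the documents: the 300 and 1200 ng/dL cuts, 5 mg steps, the 30 mg start and the 15 mg floor. Assumed:

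- 08:00 17-OHP median 600, 2000 or 5000 ng/dL, log10 SD 0.8; 13:00 median 0.5 log10 lower
- A4 correlation 0.7, one pooled A4 limit of 175 ng/dL
- 75% on fludrocortisone; 10% of reductions blocked by symptoms
- 17-OHP rise of 0.15 log10 per 5 mg reduction
- Chronocort 08:00 shift 0 or −0.6 log10
- no dropout
- r, the share of log 17-OHP variance that is stable within a person

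Simulated Week-4 down-titration on IRHC was 16–46%, which brackets the roughly 40% in SAP Section 3.

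| r | Empirical SE reduction, one main effect in the repeated measures model | Model-based SE reduction, same model | CI-width reduction, visit-specific effect (Week-28 ANCOVA) |
|---|---|---|---|
| 0.3 | 0.5–0.9% | −0.3 to 0.0% | 0.4–0.9% |
| 0.5 | 1.3–2.3% | 0.7–1.3% | 2.5–3.7% |
| 0.7 | 2.3–3.2% | 1.7–2.8% | 4.6–6.7% |
| 0.85 | 2.8–3.7% | 2.1–3.5% | 5.5–8.3% |

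Example (median 2000, r = 0.7, shift −0.6): the main-effect SE falls from 1.375 to 1.334 mg, or 3.0%. That is worth 50×(1.375/1.334)² = 53.1, about three extra participants. With the visit-specific effect, CI width falls from 5.30 to 4.94 mg. The largest empirical variance reduction with a visit-specific effect was 14.6%.

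The empirical SE fell in all 16 scenarios. A second simulation under its own assumptions gave 0.6–6% of the SE for the main effect and 0.4–16% with a by-visit term.

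**The case against.** The case for leaving the model alone has substance.

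- Titration acts on Week 4, 10 and 16 samples taken on randomized treatment, not on the baseline value. A reader might infer that participants at 300–1200 ng/dL at baseline cannot be titrated; Protocol 4.2 does not say so, and they may qualify later.
- The 13:00 sample, A4 and symptoms also drive reductions, and the Chronocort arm changes formulation and timing after baseline. It is tempting to call baseline 17-OHP the strongest available predictor of dose. No figure in the documents supports that; it is only a plausible one.
- The binary factor already carries A4 at the trigger's limits, so it is not merely 17-OHP above or below 1200.
- Participants who stop treatment return to their earlier glucocorticoid (Protocol 7.1), and their dose is analysed in hydrocortisone equivalents (SAP 5.11.3.3). The simulation had no dropout, so its gain may be optimistic.
- The endpoint is last in the hierarchy, and a common set of covariates across models is a legitimate choice.

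All of this stands, and it limits the size of the gain. It does not remove the gain or create a material downside. The blinded Data Review Meeting may consider additional covariates (Protocol Appendix 1), but SAP Version 4.0, written after blinded review, adds none here. The SAP rule that the baseline value is always a covariate covers change-from-baseline analyses only (SAP 5.11.6.2).

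**Conclusion.** The point holds as a small, inexpensive improvement in precision. As a single main effect, log baseline 17-OHP would cut the SE of the dose difference by roughly 0.5–6%; by the same conversion as in the example, 50/0.995² = 50.5 and 50/0.94² = 56.6, so between under one and about seven participants. A by-visit term gives more: up to about 15% of the variance in the main simulation, and higher if the correlation is stronger. If the correlation is about 0.2 there is no gain, or a loss of under 1% of variance. Every figure rests on that undocumented correlation.

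Two stronger readings are not supported. A reader might infer that the planned estimate is biased. It is not: randomization protects the comparison whether or not the term is included. A reader might also infer that the 1200 and 300 ng/dL cuts contradict each other. They serve different purposes: the optimal-range limit defines control, and the reference-range limit guides titration. No stated figure in the plan is wrong on this point.

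**What to change.** Before unblinding, amend SAP 5.11.5.2 and the matching row of 5.11.2.3:

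- Add log Visit 2 08:00 17-OHP as a covariate, preferably with its interaction with visit, and keep the binary control factor.
- State where the new term falls in the model-reduction sequence of SAP 5.11.4.1, which 5.11.5.2 applies to this model. Dropping the by-visit part first would be sensible.
- Leave the logistic models for the primary and first key secondary endpoints unchanged.

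If the main model can no longer be altered, specify the extended model as a sensitivity analysis.

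The cost is one degree of freedom, or three with the by-visit term (Weeks 10, 16 and 28). No new data are needed: the Visit 2 value is already the defined androgen baseline (SAP 5.2.2), and results reported as below a limit take that limit (SAP 5.2.11), so the log can be computed.
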